6.16 Proteinuria

Subjects with an abnormal urine microalbumin/creatinine ratio (> 0.3 mg/mg, > 300 mg/g or > 34 mg/mmol) that represents a change from baseline and no associated increase in creatinine, should have a repeat spot urine microalbumin/creatinine ratio performed within 2-4 weeks. If confirmed, then consideration should be made for additional evaluation after consultation with the sponsor. Additional evaluation may include a creatinine measurement and nephrology referral.

Subjects with an abnormal urine albumin/creatinine ratio (> 0.3 mg/mg, 300 mg/g or > 34 mg/mmol and representing a change from baseline) and a serum creatinine increase > 45 mMol/L (or 0.5 mg/dL) should have confirmation of both results within 2 weeks. If confirmed, the study sponsor should be immediately contacted. Agreement on further management should be agreed between the investigator and study sponsor.

6.17 Creatine Phosphokinase (CPK) Elevation

A Grade 3 or higher elevation in CPK should result in a repeat assessment within 2 to 4 weeks to ensure the result is transient or due to exercise and will not require a change in study treatment. A history regarding use of drugs known to cause increase of CPK (such as statins) physical activity or exercise preceding the CPK evaluation should be obtained. Grade 4 elevations in CPK should have a repeat assessment after the subject has abstained from exercise for > 24 hours. For persistent Grade 4 CPK elevations that are considered possibly or probably related to the study drug, study drug should be discontinued and the subject withdrawn from the study.

CONFIDENTIAL

6.18 Storage and analysis of samples

See appendix 1 for details of assessments required.

All samples (with the exception of PK & PMBC samples) will be analysed at each local site laboratories and destroyed after analysis. PK samples will be shipped and analysed by a central laboratory in the UK. PBMC samples will be shipped and analysed by a central laboratory in Spain.

Collection and processing and storage instructions for all samples will be detailed in a separate Laboratory Manual.

6.19 Virological failure

Virological failure is defined as two consecutive measurements of plasma viral load above 50 copies/ml separated by at least 14 days during the assigned treatment. Note: If the initial sample analysis returns result of >50c/mL, the remainder of the sample should be re-analysed, if possible. Only if the repeat analysis produces a second result of >50c/mL, or if re-analysis is not possible, the patients should be recalled for retesting. The remainder of the retesting sample should be analysed if the retesting analysis produces a result of >50c/mL. In case of virological failure a resistance study will be conducted in the local lab of each centre. Note: resistance test should be performed from the suspect virological failure visit sample and from the confirmatory visit when available.

Pharmacokinetic testing should also be carried out in the event of viral failure.

Patients should discontinue study medication and receive rescue medication at investigators discretion.

Therapeutic failure includes virological failure, change in treatment for any reason, consent withdrawal, loss to follow-up or death.

6.20 End of trial

The end of the trial is defined as the date of the last visit (i.e. Follow-up visit) of the last subjects undergoing the trial.

CONFIDENTIAL

The sponsor must notify the Competent Authority and main REC of the end of a clinical trial within 90 days of its completion.

Note: The DSMB will elect stopping criteria as defined in the DSMB charter. If the study ends early by recommendation from the DSMB or for any other reason, the sponsor will notify the Competent Authorities and Ethics Committees of the reasons for the premature termination.

7 TRIAL MEDICATION

7.1 Name and description of investigational medicinal product(s)

Subjects will discontinue their usual boosted protease inhibitor or other ARV regimen (including Anatomical Therapeutic Chemical Classification System codes: JO5AB, JO5AE, JO5AF, JO5AG, JO5AR, JO5AX) and will switch to DTG plus RPV at baseline or week 48.

ViiV will supply Dolutegravir 50mg / Rilpivirine 25mg FDC tablets in the form of “Juluca” (which will be labelled in accordance with annex 13 requirements).

From baseline to week 96 or from week 48 to week 96, as randomised, participants will take a DTG/ RPV combined tablet once a day orally. Participants in the deferred group will continue to take their usual ARV regimen from baseline to week 48 until they switch to DTG/ RPV combined tablet.

The early switch group will be dispensed a supply of DTG/RPV combined tablets at baseline, week 4, 12 and 24. Both the early switch group and deferred switch group will be dispensed supply of DTG/RPV combined tablets at week 48, 52 and 72. Please refer to the study specific pharmacy manual for more information. Note, dispensing weeks may be modified with sponsor’s approval and in line with local regulations (if required). Prior to switch subjects will continue to be dispensed standard care boosted protease inhibitor or other ARV regimen.

7.2 Reference Safety Information

The Reference Safety Information (RSI) for the DTG/RPV FDC is the Juluca Summary of Product Characteristics (section 4.8 Undesirable effects). Please refer to this for further information on contraindicated treatments, drug interactions and adverse events expectedness. For pre-switch reference

CONFIDENTIAL

safety information, investigators are to refer to the SmPC (per ATC code) for information on expectedness, contraindicated treatments, drug interactions and adverse events.

7.3 Drug storage and supply

Investigators are to ensure that the investigational product will only be used in accordance with the protocol. Drug supplies will be kept in a secure, limited access storage area under the recommended storage conditions (see pharmacy manual) accessible only to those authorised by the investigator to dispense to eligible subjects.

The investigator will ensure that records are maintained showing the receipt and disposition of all study supplies. A drug accountability log will be kept with the investigational supplies for reconciliation purposes. This should be used to record the trial identification of the subject to whom the investigational product was dispensed, the date and quantity of investigational product dispensed, and the quantity of investigational product unused/returned by the subject. This will be verified by the study monitor.

Partially used or empty containers may be destroyed by pharmacy/designee at local site after the study monitor has completed a final inventory to verify the quantity returned. The pharmacy/designee are required to document destruction for verification by the sponsor.

7.4 Preparation and labelling of Investigational Medicinal Product

Dolutegravir & Rilpivirine combined therapy tablets will be labelled with Annex 13 compliant labels and QP certified by Almac Group Ltd who will provide supply directly to each site on request of the sponsor.

Boosted PIs (or other antiretroviral combination regimen) will be sourced from usual commercial supply as per standard practice.

Further information can be found in the pharmacy manual.

CONFIDENTIAL

7.5 Dosage schedules

Experimental arm (Baseline visit switch group): One combined Dolutegravir 50mg /Rilpivirine 25mg tablet taken orally once daily (at the same time) for up to 96 weeks with a meal. NB: A high protein drink is not suitable substitute for a meal.

Control arm (deferred week 48 switch group): patients will continue their current boosted PI regimen (or other antiretroviral combination regimen) for 48 weeks. Patients will then be switched to one combined Dolutegravir 50mg /Rilpivirine 25mg tablet taken orally once daily for up to 48 weeks with a meal.

7.6 Dosage modifications

There are no dose modifications for this trial. Please refer to section 6 for withdrawal and stopping rules.

7.7 Known drug reactions and interaction with other therapies

Dolutegravir

See section 8.3 and reference safety information.

Dofetilide is prohibited as DTG may inhibit its renal tubular secretion resulting in increased dofetilide concentrations and potential for toxicity. Strong inducers of DTG metabolism such as carbamazepine must be avoided.

Rilpivirine

See section 8.3 and reference safety information.

Medications that affect rilpivirine and that are affected by the use of rilpivirine accordingly must be reviewed by the investigator and/or avoided.

CONFIDENTIAL

7.8 Concomitant medication

DTG/RPV FDC is contraindicated in combination with the following:

- antiarrhythmic agents dofetilide or pilsicainide (DTG may inhibit its renal tubular secretion resulting in increased dofetilide concentrations and potential for toxicity)
- fampridine (also known as dalfampridine)
- anticonvulsants carbamazepine, oxcarbazepine, phenobarbital, phenytoin
- antimycobacterials rifampicin, rifapentine
- proton pump inhibitors (such as omeprazole, esomeprazole, lansoprazole, pantoprazole, and rabeprazole)
- systemic dexamethasone (except as a single dose treatment)
- St John's wort (*Hypericum perforatum*)

7.9 Prior Concomitant Therapy

All medications (prescriptions or over-the-counter medications, herbal and naturopathic products) continued at the start of the treatment or started during the treatment must be documented (dose, frequency, stop and start dates). Unnecessary changes or additions to any concomitant medication should be avoided.

Warnings and precautions regarding contraindicated concomitant medications, AE and drug interactions can be found above or within reference safety information.

NOTE! Caution must also be applied when patients take medications that inhibit CYP3A as this may lead to excessive exposure of rilpivirine.

Any medications excluded in the Exclusion criteria will not be permitted in this study. However, if there is a clinical need for the use of any of these medications then the participant may need to be discontinued from the study. If this is the case, then the investigator should discuss with the CI or Sponsor trials team, but the final decision remains that of the site investigator.

All concomitant medication information will be captured in the participant's Case Report Forms.

7.10 Trial restrictions

Please refer to inclusion & exclusion criteria listed in sections 5.1 & 5.2.

CONFIDENTIAL

7.11 Assessment of compliance

Adherence during the trial will be monitored by subject questioning regarding missed tablets at each visit. If poor adherence is suspected based on tablet counts, this will be discussed with the subject to confirm lack of adherence i.e. via subject interview. The outcome of this questioning should be documented in the patient notes. If the subject misses a significant number of tablets, this should be reported to the study monitor. All subjects should return unused medication and containers at weeks 72 and 96 (plus at weeks 4, 12, 24 and 48 for the experimental arm) for pharmacy accountability purposes (see section 7.3).

7.12 Provision of treatment after the end of the trial

No post trial medication will be provided to patients. Following study completion, patients are to receive treatment as per local standard of care.

8 PHARMACOVIGILANCE

8.1 Definitions

Term	Definition
Adverse Event (AE)	Any untoward medical occurrence in a participant to whom a medicinal product has been administered, including occurrences which are not necessarily caused by or related to that product.
Adverse Reaction (AR)	
An untoward and unintended response in a participant to an investigational medicinal product which is related to any dose administered to that participant.
 
The phrase “response to an investigational medicinal product” means that a causal relationship between a trial medication and an AE is at least a reasonable possibility, i.e. the relationship cannot be ruled out.
 
All cases judged by either the reporting medically qualified professional or the Sponsor as having a reasonable suspected causal relationship to the trial medication qualify as adverse reactions

CONFIDENTIAL

Serious Adverse Event (SAE)	
A serious adverse event is any untoward medical occurrence that:
 
• results in death• is life-threatening• requires inpatient hospitalisation or prolongation of existing hospitalisation• results in persistent or significant disability/incapacity• consists of a congenital anomaly or birth defect 
Other ‘important medical events’ may also be considered serious if they jeopardise the participant or require an intervention to prevent one of the above consequences.
 
NOTE: For the purposes of this study, all AEs meeting liver stopping criteria (as defined in section 6.13) associated with dolutegravir and all events of possible drug-induced liver injury (DILI) with hyperbilirubinemia defined as ALT \geq 3X_{ULN} and bilirubin \geq 2X_{ULN} (>35% direct) are also considered serious and must be reported (see Section 8.3)
 
NOTE: The term “life-threatening” in the definition of “serious” refers to an event in which the participant was at risk of death at the time of the event; it does not refer to an event which hypothetically might have caused death if it were more severe.

Serious Adverse Reaction (SAR)	
An adverse event that is both serious and, in the opinion of the reporting Investigator, believed with reasonable probability to be due to one of the trial treatments, based on the information provided.

Suspected Unexpected Serious Adverse Reaction (SUSAR)	
A serious adverse reaction, the nature and severity of which is not consistent with the information about the medicinal product in question set out:
 
The reference safety information for the DTG/RPV FDC is contained within Juluca Summary of Product Characteristics (SmPC) at section 4.8 Undesirable effects, please refer to this document for further information on contraindicated treatments, drug interactions and adverse events expectedness.

“Severe” is often used to describe intensity of a specific event, which may be of relatively minor medical significance. “Seriousness” is the regulatory definition supplied above.

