 - Male partner sterilisation confirmed prior to the female subject's entry into the study, and this male is the sole partner for that subject;
 - Approved hormonal contraception (see appendix 4 for a listing of examples of approved hormonal contraception);
 - Any other method with published data showing that the expected failure rate is <1% per year;
 - Any contraceptive method must be used consistently and for at least 2 weeks after discontinuation of IP.
9. If a heterosexually active male, he is using effective birth control methods and is willing to continue practising these birth control methods during the trial and until follow-up visit.
10. Subjects currently receiving DTG or RPV, but not both, can be included.

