6.13 Liver Chemistry Stopping and Follow up Criteria

Liver chemistry threshold stopping criteria have been designed to assure subject safety and to evaluate liver event etiology during administration of study drug and the follow-up period. Study drug must be stopped if any of the following liver chemistry criteria are met:

- ALT $\geq 3 \times \text{ULN}$ and bilirubin $\geq 2 \times \text{ULN}$ (>35% direct bilirubin; bilirubin fractionation required)

NOTE: serum bilirubin fractionation should be performed if testing is available. If testing is unavailable, record presence of detectable urinary bilirubin on dipstick, indicating

CONFIDENTIAL

direct bilirubin elevations and suggesting liver injury. If testing is unavailable and a subject meets the criterion of total bilirubin ≥ 2 xULN, then the event meets liver stopping criteria and should be reported as an SAE. If INR is obtained, include values on the SAE form. INR elevations >1.5 suggest severe liver injury.

- ALT ≥ 8 xULN;
- ALT ≥ 3 xULN (if baseline ALT is $<$ ULN) with symptoms or worsening of acute hepatitis or hypersensitivity such as fatigue, nausea, vomiting, right upper quadrant pain or tenderness, fever, rash, or eosinophilia, OR;
- ALT ≥ 3 x baseline ALT with symptoms or worsening of acute hepatitis or hypersensitivity such as fatigue, nausea, vomiting, right upper quadrant pain or tenderness, fever, rash, or eosinophilia;
- ALT ≥ 5 xULN and < 8 xULN that persists > 2 weeks (with bilirubin < 2 xULN and no signs or symptoms of acute hepatitis or hypersensitivity);
- ALT ≥ 5 xULN but < 8 xULN and cannot be monitored weekly for > 2 weeks;

Subjects who develop ALT ≥ 5 xULN should be followed weekly until resolution or stabilisation (ALT < 5 xULN on 2 consecutive evaluations).

When liver chemistry stopping criterion is met, the following procedures must be followed:

- **Immediately** hold dolutegravir and rilpivirine. If a causal relationship between the liver event and dolutegravir and rilpivirine cannot be ruled out, then dolutegravir and rilpivirine must be permanently discontinued and the Subject not rechallenged due to the risk of a recurrent reaction. If the liver event has a clear underlying alternative cause, other than drug-induced liver injury, then Drug Restart may be considered (see below).
- Report the event to the study sponsor pharmacovigilance team within 24 hours of learning its occurrence (see section 8.3)

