8.2.1 Assessment of Intensity

Severity should be recorded and graded according to the AIDS Clinical Trial Group (ACTG) Grading Scale (*appendix 2*).

Note: There is a distinction between the seriousness and the intensity of an adverse event. Severe is a measure of intensity; thus, a severe reaction is not necessarily a serious adverse event. For example, a headache may be severe in intensity but would not be classified as serious unless it meets one of the seriousness criteria for serious events.

All events deemed to be Grade 4 (potentially life threatening) according to the ACTG grading scale should be

CONFIDENTIAL

routinely reported as a serious adverse event. However, there may be occasions where in the investigator's clinical judgement they do not consider the event to be life threatening therefore they do not consider the event to meet the definition of an SAE. In these cases, the investigator must document clearly in the participants source documentation that the Grade 4 event has been assessed and why in their clinical judgement they do not consider the event to be life threatening.

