8.2.4 Serious Adverse Events (SAE) & reportable events

See SAE definition within section 8.1.

Liver stopping criteria & clinically significant liver chemistry evaluation adverse events.

All AEs meeting liver stopping criteria, clinically significant liver chemistry elevations (as defined in section 6.13) associated with dolutegravir and all events of possible drug-induced liver injury (DILI) with hyperbilirubinemia defined as ALT \geq 3X_{ULN} and bilirubin \geq 2X_{ULN} (>35% direct) are considered serious for the purposes of this clinical trial and must be reported. See section 8.4 for reporting guidelines. NOTE: bilirubin fractionation should be performed if testing is available. If testing is unavailable, record presence of detectable urinary bilirubin on dipstick indicating direct bilirubin elevations and suggesting liver injury. If testing is unavailable and a subject meets the criterion of total bilirubin \geq 2X_{ULN}, then the event should still be reported as an SAE. If INR is obtained, include values on the SAE form. INR elevations >1.5 suggest severe liver injury.

Suicidality-related adverse event

If any subject experiences a possible suicidality-related adverse event (PSRAE) while participating in this study that is considered by the Investigator to meet above described definitions, this should be reported to the Sponsor. See section 8.4 for reporting format & timeline. A PSRAE may include, but is not limited to, an event that involves suicidal ideation, a preparatory act toward imminent suicidal behaviour, a suicide attempt, or a completed suicide. The investigator should exercise his or her medical and scientific judgment in deciding whether an event is possibly suicide related.

CONFIDENTIAL

Pregnancy

There is no requirement to report pregnancies in female partners of male participants. Please see risk section 1.1 for further details.

Trial subject pregnancies should be reported as per table 2

Overdose

All participants should be counselled about the importance of taking the medications as prescribed and they should understand the quantity of medicine they should be taking. Participants must be told to contact the clinic immediately if they take too much medication. If the overdose fits the criteria of an SAE (see Section 8) it should be reported appropriately. See table 2 for SAE reporting format and timelines.

Deaths

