8.3 Recording and reporting of SAEs AND SUSARs

8.3.1 Reporting requirements

All SAEs occurring from consent to 28 days post cessation of trial treatment must be recorded & reported by site (see table 2 for forms to be used and reporting timeline).

The investigator must immediately and not later than in 24 hours, report to the sponsor; all serious adverse events by emailing [contact] or by sending a fax to [contact].

For each SAEs / SUSARs the following information will be collected in a dedicated safety event reporting form (SERF):

CONFIDENTIAL

- full details in medical terms and case description
- event duration (start and end dates, if applicable)
- action taken
- outcome
- seriousness criteria
- causality (i.e. relatedness to trial drug / investigation), in the opinion of the investigator
- whether the event would be considered expected or unexpected.

Any change of condition or other follow-up information should be provided to the Sponsor as soon as it is available or at least within 24 hours of the information becoming available. Query responses should be also provided to the Sponsor within the requested timelines. Follow-up information and Query Response must be sent emailing [contact] or by sending a fax to [contact]. Events will be followed up until the event has been resolved or a final outcome has been reached.

All SAEs assigned by the PI or delegate (or following central review) as both suspected to be related to IMP-treatment and unexpected, will be classified as SUSARs and will be subject to expedited reporting to the Competent Authority. The Sponsor will inform CAs, ECs and ViiV of SUSARs within the required expedited reporting timescales.

Table 2: Safety Reporting Format & Timelines

Safety Data	Reporting Format	Timeline
All SAEs arising during the Clinical Trial, regardless of Investigator/designee causality assessments against IMP(s)	SERF	Site to report to sponsor within 24 hours of first becoming aware of the event.

CONFIDENTIAL

Pregnancy information for all female Clinical Trial Subjects who become pregnant while participating in the Clinical Trial and following exposure to an IMP.
	
SERF
	
Site to send to sponsor within 24 hours of first becoming aware of the pregnancy or the pregnancy outcome.

The subject will also be followed to determine the outcome of the pregnancy (including information on the status of the mother and child), which will also be reported to sponsor.
		

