
All liver events meeting the criteria for an SAE, including all events of possible drug-induced liver injury (DILI) with hyperbilirubinemia defined as ALT \geq 3X_{ULN} and bilirubin \geq 2X_{ULN} (>35% direct)
	
SERF
	
The SAE form must be completed and reported to the sponsor within 24 hours.

All Liver Chemistry Elevations that meet Liver Stopping Criteria (as defined in the Protocol), regardless of Investigator/designee causality assessments against IMP(s); and whether or not the event and/or associated signs and symptoms meet definitions of seriousness as outlined above
	
Liver Event CRF Modules i.e. VHL liver event CRF, liver imaging and/or liver biopsy CRFs
	
Site to complete the Liver event CRF modules and send to sponsor within one week of first becoming aware of the event

CONFIDENTIAL

Suicidality-related adverse events (PSRAEs) (as defined in the Protocol) that met the criteria for an SAE.	SERF PSRAE CRF Module	The SAE form must be completed and reported to the sponsor within 24 hours. The PSRAE CRF Module should be completed and reported to the sponsor within one week of the investigator diagnosing a possible suicidality-related adverse event
Deaths	Any AE, adverse reaction or unexpected adverse reaction that results in death should be reported as an SAE on an SERF	Site to report to sponsor within 24 hours of first becoming aware of the event.
Overdose	If the overdose fits the criteria of an SAE (see Section 8) it should be reported appropriately on an SERF	Site to report to sponsor within 24 hours of first becoming aware of the event.

All safety reports and reportable events listed on the above table (including Investigator causality) assessment should be reported in English to the sponsor.

Reporting Period

The SAEs, and pregnancy reports that are subject to the above reporting provisions are those that occur following the consent through to 28 days post cessation of trial treatment.

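### Before week 48 some liver-stopping events can be SAEs on DTG/RPV but not in a control participant taking no dolutegravir, while SAP 9(g) compares SAE rates between arms (minor)

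*Protocol*

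**What the plan says.** Protocol 8.1 adds two liver categories to the general seriousness criteria. The first is "all AEs meeting liver stopping criteria (as defined in section 6.13) associated with dolutegravir". The second is possible drug-induced liver injury (DILI) with hyperbilirubinaemia, which carries no drug qualifier.

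Protocol 8.2.4 restates the rule with different punctuation: "All AEs meeting liver stopping criteria, clinically significant liver chemistry elevations (as defined in section 6.13) associated with dolutegravir".

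Two other provisions decide who is covered. In the control arm "patients will continue their current boosted PI regimen (or other antiretroviral combination regimen) for 48 weeks" (Protocol 7.5). Inclusion criterion 10 (Protocol 5.1) states: "Subjects currently receiving DTG or RPV, but not both, can be included". A control participant may therefore already be on dolutegravir, but need not be.

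SAP 9(g) lists SAEs among the events whose incidence rates are compared between treatment groups by Poisson regression. It gives no rule for events that are serious only through the liver note, and it plans no analysis of the liver event CRF.

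**The concern.** A between-arm comparison of SAE rates is fair only if the same clinical event receives the same label in both arms. Here one route to the label depends on the drug taken, and until week 48 the drug is what the randomisation varies. The same rise in ALT can count as an SAE on DTG/RPV and as a non-serious AE on a boosted PI. A dolutegravir-specific rule may suit pharmacovigilance. The difficulty comes from using the resulting label as a comparative outcome. At stake is a small, one-directional distortion of one secondary safety comparison, to the disadvantage of DTG/RPV.

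**Working it through.** The plan states no figure on this point, so the check is mainly a comparison of texts, followed by simple arithmetic on scale.

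**1. Which stopping events need the dolutegravir route?** Protocol 6.13 lists six criteria.

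| Criterion in 6.13 | Raised bilirubin required? |
|---|---|
| ALT ≥3×ULN with bilirubin ≥2×ULN (>35% direct) | Yes |
| ALT ≥8×ULN | No |
| ALT ≥3×ULN, baseline below ULN, with symptoms | No |
| ALT ≥3×baseline, with symptoms | No |
| ALT 5 to 8×ULN for more than 2 weeks | No |
| ALT 5 to 8×ULN, weekly monitoring not possible | No |

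Only the first coincides with the DILI limb, which applies to any regimen. Five of the six rely on the dolutegravir-linked limb, unless another route to seriousness applies.

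**2. Which routes are open to both arms?** The general criteria of 8.1, including important medical events; DILI with hyperbilirubinaemia; and, under 8.2.1, "All events deemed to be Grade 4 (potentially life threatening) according to the ACTG grading scale", which are routinely reported as SAEs unless the investigator documents otherwise. The unequal group is what remains after these.

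**3. What does 'associated' mean?** Protocol 8.2 uses the word both for timing and for suspected cause.
- Temporal reading: any stopping event in a person taking dolutegravir is labelled.
- Causal reading: the label also needs the investigator's attribution, in an open-label trial.
- Either reading excludes a control participant who takes no dolutegravir.

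**4. Does 8.2.4 settle it?** No. Its comma allows the qualifier to attach only to the chemistry elevations. All stopping events would then be serious in both arms, which conflicts with 8.1. If the qualifier covers both items, 8.2.4 agrees with 8.1.

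**5. Direction.** Let B be the rate of SAEs by routes open to both arms, r the rate of events in the unequal group, a the share of those events labelled among people taking dolutegravir (1 on the temporal reading), and f the share of control participants on dolutegravir. Suppose B, r and a are the same in both arms. Then to week 48:

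- DTG/RPV labelled rate = B + a·r
- control labelled rate = B + f·a·r
- difference = a·r·(1 − f), which is never negative.

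**6. Scale.** Planned numbers are 100 and 50 (Protocol 9.1); a year is 365.25/7 = 52.18 weeks; no dropout.

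- Person-years to week 48: 100 × 48/52.18 = 92.0 and 50 × 48/52.18 = 46.0.
- One control event equals 100/46.0 = 2.17 per 100 person-years.
- Expected control events without the label, at a = 1: 46.0 × (r/100) × (1 − f). This is below one whenever r·(1 − f) is below 2.17 per 100 person-years.

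The documents give neither r nor f. With r assumed at 0.5 to 2 per 100 person-years and f at 0 to 0.5, the result runs from 46.0 × 0.005 × 0.5 = 0.11 to 46.0 × 0.02 × 1 = 0.92 control events.

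**7. After week 48.** Control participants who switch take DTG/RPV and fall under the same rule. SAP 4.1 switches only those with virological success, so an unswitched control participant not on dolutegravir would keep the unequal label.

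**The case against.** The strongest reply is that stopping events already follow the SAE route in both arms. Protocol 6.13 requires a report within 24 hours and refers to section 8.3, with no dolutegravir qualifier on that step. But the next item in 6.13 names only DILI with hyperbilirubinaemia as reportable as an SAE. Table 2 in 8.3.1 likewise keeps the SERF for liver events that meet SAE criteria. Other stopping events go to the liver event CRF, "regardless of Investigator/designee causality assessments against IMP(s); and whether or not the event and/or associated signs and symptoms meet definitions of seriousness". That secures the data but assigns no SAE label. The procedure in 6.13 also opens with an instruction to "hold dolutegravir and rilpivirine. If a causal relationship between the liver event and dolutegravir and rilpivirine cannot be ruled out", so it is written around the study drug.

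Other parts of the reply stand:

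- The reading of 8.1 is not certain, and one reading of 8.2.4 removes the asymmetry and leaves a drafting conflict.
- On the causal reading, some DTG/RPV-arm events also go unlabelled.
- The grade 3/4 AE comparison in SAP 9(g) and the ALT, AST and bilirubin comparisons in SAP 9(h) do not use the SAE label, so a hepatic difference would not be hidden.
- The liver exclusions in Protocol 5.2 remove many participants at risk.

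A reader might infer that control liver events go unreported, or that no control liver event can be an SAE. The documents support neither: Table 2 covers every stopping event, the routes in step 2 apply in both arms, and control participants on dolutegravir are covered by the note.

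**Conclusion.** The concern holds as a minor point, with moderate confidence. Following 8.1 as written, SAE ascertainment before week 48 is unequal for one narrow group of events: those that meet a 6.13 criterion, have no hyperbilirubinaemia, are not reported as Grade 4 SAEs and meet no general seriousness criterion. With equal true rates and equal labelling among people taking dolutegravir, the effect on SAP 9(g) can only raise the DTG/RPV rate relative to control.

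Probably fewer than one control event is affected. That rests on the assumed rates in the working and not on any figure in the documents, so no distorted rate ratio can be put forward. A reader might infer that the safety comparison as a whole is unsound or that efficacy is touched. Neither follows: one secondary comparison is involved, other liver analyses are free of the label, and the primary endpoint is unaffected.

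**What to change.** **Protocol.** In 8.1 and 8.2.4, delete the three words that tie the rule to dolutegravir, so that it covers any antiretroviral regimen in either arm. This also removes the conflict between the two sections. In Table 2, state that the liver event CRF is completed in both arms from baseline.

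**SAP 9(g).** Add: 'All events meeting the stopping criteria of protocol section 6.13 will be tabulated by arm, before and after week 48, from the liver event CRF.'

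**If the protocol is not amended,** also add: 'A sensitivity comparison of SAE incidence will omit stopping events that are serious solely through the dolutegravir-linked limb of protocol section 8.1. Possible DILI with hyperbilirubinaemia is kept, because it applies to both arms.'

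**Cost.** A few words in the protocol, at the next amendment, and one or two sentences in the SAP. The amended rule would bring a few more SAE reports from control participants. The tabulation uses a form that already exists. The sensitivity comparison needs one check: Protocol 8.3.1 says that the SERF records seriousness criteria, but the documents do not show whether events serious only by study rule can be told apart from important medical events.
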